9.5. Treatment Compliance

[figure not shown]
Self-dosing compliance will be evaluated at each clinic visit by pill count and subject's diary report of dosing. Subjects will be instructed to call the Investigator's office before taking the next dose of study drug if they notice any symptoms of hypotension, bradycardia, and/or orthostasis, especially when standing from a sitting or lying position. The study physician or assigned staff will determine if the next dose should be delayed, skipped, or the subject should be seen. Any change in prescribed dosing will be recorded in source documents and confirmed also by pill count and subject report at the next visit.

10. STUDY DRUG MATERIALS AND MANAGEMENT

10.1. Study Drug

10.1.1. Lofexidine Hydrochloride

Lofexidine hydrochloride (HCl) tablets contain lofexidine, which is a selective adrenergic $\alpha 2$ receptor agonist, as the HCl salt. Lofexidine HCl is chemically designated as 2-[1-(2,6-dichlorophenoxy)ethyl]-4,5 dihydro-1*H*- imidazole monohydrochloride with a molecular formula of C₁₁H₁₂Cl₂N₂O•HCl. Its molecular weight is 295.6 and its structural formula is:

The description of the study drug is presented in Table 8.

	Investigational Product
Product Name:	Lofexidine HCl (LUCEMYRA TM)
Dosage Form:	Tablet
Unit Dose:	Each LUCEMYRA tablet is 0.18 mg. See Section 9.2.3 for dose adjustments and taper regimens.
Route of Administration:	Oral
Physical Description:	Lofexidine HCl is a synthetic product and has the chemical designation of 2 [1-(2,6-dichlorophenoxy)ethyl]-4,5 dihydro-1H- imidazole monohydrochloride. Lofexidine HCl will be supplied in peach-colored tablets containing 0.18 mg of active medication for oral administration.
Manufacturer:	
HCl = hydrochloride;	QID = 4 times daily

10.1.2. Placebo

Placebo tablets will be identical in appearance to LUCEMYRA tablets.

Protocol

10.2. Study Drug Packaging and Labeling

The study drug will be packaged in bottles of 112 tablets. The package product label will include the following information:

- Sponsor's name
- Protocol number
- A unique package number for purposes of study drug accountability
- A description of the study drug (ie, "Lofexidine or Placebo")
- Statement that the study drug is for investigational use only

10.3. Study Drug Storage

Lofexidine HCl and placebo should be stored in the original package at controlled room temperature 20 to 25°C (68 to 77°F), with excursions permitted between 15 to 30°C (59 to 86°F).

10.4. Study Drug Preparation

See Section 9.2.2.

10.5. Administration

See Section 9.2.3.

10.6. Study Drug Accountability

All study drug required for completion of this study will be provided by the Sponsor. Accurate recording of all study drug received, dispensed, administered, and returned will be maintained by study site personnel. All study drug is to be used only as described by this study protocol by appropriately licensed Investigators named in Form FDA 1572.

Study staff should retain the original individual containers, including those empty, partially empty, or full. Study drug must be inventoried. If any study drug is lost or damaged, its disposition should be documented. Unused study drug will be retained at the participating sites to enable a full study drug inventory by the sites' respective monitors

10.7. Study Drug Handling and Disposal

At the end of the study, all unused study drug must be inventoried. If any study drug is lost or damaged, its disposition should be documented. Unused study drug will be retained at the participating sites pending instructions for disposition by the Sponsor at the end of the study.

11. ASSESSMENTS OF EFFECTIVENESS

11.1. Numeric Rating Scale (NRS) of Pain Intensity

The NRS of pain intensity is a unidimensional, segmented numeric version of the visual analog scale. A subject selects a whole number (0 to 10) that best indicates the intensity of his/her pain. The format consists of a horizontal line which is anchored by terms defining pain levels where 0 represents no pain and 10 represents worst pain imaginable.

At bedtime, subjects will answer the following questions regarding daily pain intensity:

How would you rate the average pain due to your current chronic pain condition over the last 24 hours?

How would you rate the worst pain due to your current chronic pain condition over the last 24 hours?

Sometimes when people come off opioids, they feel aches and pains all over their body. How would you rate the average pain, all over your body over the last 24 hours?

Sometimes when people come off opioids, they feel aches and pains all over their body. How would you rate the worst pain, all over your body over the last 24 hours?

NRS chronic pain scales will be completed daily at home before bedtime beginning at Screening through the 30-day follow-up phone call and at clinic visits (and Early Termination, if applicable). NRS all over body pain scales will be completed at home before bedtime beginning on Day 1 through the EOS Visit and at clinic visits (and Early Termination, if applicable). NRS scales completed at the Day 1 Visit (Visit 1) should be completed prior to the first dose of study drug.

A copy of the NRS is provided in Section 16.1.

11.2. Clinical Opiate Withdrawal Scale (COWS)

The COWS will be used to assess effectiveness of LUCEMYRA in alleviation of opioid withdrawal [Wesson 2003]. The COWS is a clinician-administered instrument that rates 11 common opioid withdrawal signs and symptoms. These include: resting pulse rate; sweating; restlessness; pupil size; bone or joint aches; runny nose or tearing; gastrointestinal upset; tremor; yawning; anxiety or irritability; and gooseflesh skin. Lower total scores indicate a more positive clinical outcome.

The COWS completed at the Day 1 Visit (Visit 1) should be completed prior to the first dose of study drug.

A copy of the COWS assessment tool is provided in Section 16.4.

11.3. Short Opiate Withdrawal Scale of Gossop (SOWS-Gossop)

The SOWS-Gossop scale assesses subjective symptoms of opioid withdrawal [Vernon 2016, Gossop 1990]. It is a subject-rated scale consisting of 10 items that are scored on a 4-point scale of 0 = none, 1 = mild, 2 = moderate, and 3 = severe (minimum score of 0, maximum score of 30) (Table 9). The overall score is the simple sum of the 10 item scores. Lower observed values in

SOWS-Gossop scores indicate a more positive clinical outcome. The SOWS-Gossop will be completed daily beginning at Day 1 at home at bedtime and at clinic visits (and Early Termination, if applicable). The SOWS-Gossop completed at the Day 1 Visit (Visit 1) should be completed prior to the first dose of study drug.

	Score			
Condition	None	Mild	Moderate	Severe
Feeling sick	0	1	2	3
Stomach cramps	0	1	2	3
Muscle spasms/twitching	0	1	2	3
Feeling of coldness	0	1	2	3
Heart pounding	0	1	2	3
Muscular tension	0	1	2	3
Aches and pains	0	1	2	3
Yawning	0	1	2	3
Runny eyes	0	1	2	3
Insomnia/problem sleeping	0	1	2	3

Table 9:SOWS-Gossop Scoring Method

SOWS-Gossop = Short Opiate Withdrawal Scale of Gossop

Note: possible score range is 0 to 30.

A copy of the SOWS-Gossop is provided in Section 16.5.

11.4. Subjective Opiate Withdrawal Scale of Handelsman (SOWS-H)

The SOWS-H scale assesses subjective symptoms of opioid withdrawal [Handelsman 1987]. It is a subject-rated scale consisting of 19 items that are scored on a 5-point scale of 0 = not at all, 1 = a little, 2 = moderately, 3 = quite a bit, and 4 = extremely. The overall score is the simple sum of the 19 item scores. Lower observed values in SOWS-H scores indicate a more positive clinical outcome. The SOWS-H will be completed daily beginning at Day 1 at home at bedtime and at clinic visits (and Early Termination, if applicable). The SOWS-H completed at the Day 1 Visit (Visit 1) should be completed prior to the first dose of study drug.

Item 16 of the SOWS-H was rephrased to be more appropriate for this population [FDA 2014].

A copy of the SOWS-H is provided in Section 16.6.

11.5. Hospital Anxiety and Depression Scale (HADS)

The HADS is a self-reported screening tool for anxiety and depression in nonpsychiatric clinical populations. The scale consists of 14 items (7 each for anxiety and depression), each rated on a 4-point scale. Responses are based on the relative frequency of symptoms over the preceding week. Possible scores range from 0 to 21 for each subscale. An analysis of scores on the 2 subscales supported the differentiation of each mood state into 4 ranges: non-cases (scores 0 to

7), mild cases (scores 8 to 10), moderate cases (scores 11 to 15), and severe cases (scores 16 or higher) [Zigmond 1983].

A copy of the HADS is provided in Section 16.7.

11.6. Insomnia Severity Index (ISI)

The ISI is a 7-item self-report questionnaire assessing the nature, severity, and impact of insomnia. The recall period is the last 2 weeks and the dimensions evaluated are: severity of sleep onset, sleep maintenance and early morning awakening problems, sleep dissatisfaction, interference of sleep difficulties with daytime functioning, noticeability of sleep problems by others, and distress caused by the sleep difficulties. A 5-point Likert scale is used to rate each item, yielding a total score ranging from 0 to 28. The total score is interpreted as follows: absence of insomnia (0-7); sub-threshold insomnia (8-14); moderate insomnia (15-21); and severe insomnia (22-28) [Bastien 2001].

A copy of the ISI is provided in Section 16.8.

11.7. Modified Clinical Global Impression – Subject Version (MCGI-S)

The MCGI-S includes 2 items:

- A 7-point scale that allows subjects to rate the severity of opiate withdrawal symptoms.
- A 4-point scale that allows subjects to rate the degree of side effects from their study drug.

The MCGI-S will be completed once daily beginning at Day 1 at home at bedtime and at clinic visits (and Early Termination, if applicable).

A copy of the MCGI-S is provided in Section 16.9.

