6.4. Assessment Tools Used to Achieve Objectives

The assessment tools used to achieve the study objectives are presented in Table 7. Effectiveness and safety endpoints, based on these assessment tools, are defined in Section 7.2.

Objective	Assessment Tools
Primary Objective	
Evaluate the safety and tolerability of LUCEMYRA versus placebo when used during an opioid taper in subjects with chronic non-cancer pain	AE reports, clinical laboratory assessments, monitoring of DILI, vital signs, and C-SSRS
Secondary Objectives	
Estimate the difference between treatment groups in measures related to opioid withdrawal and completion of opioid discontinuation when tapered	Taper completion status, reduction in opioid use, urine drug screen, COWS, MCGI-R, MCGI-S, SOWS-Gossop, SOWS-H
Estimate the difference between treatment groups in measures of effectiveness in pain relief, quality of life, and treatment satisfaction	EQ-5D-5L, HADS, ISI, NRS, SF-36, subject satisfaction, and use of rescue medication for pain

 Table 7:
 Assessment Tools Used to Achieve Objectives

AE = adverse event; COWS = Clinical Opiate Withdrawal Scale; C-SSRS = Columbia-Suicide Severity Rating Scale; DILI = drug-induced liver injury; EQ-5D-5L = EuroQol 5-Dimension 5-Level; HADS = Hospital Anxiety and Depression Scale; ISI = Insomnia Severity Index; MCGI-R = Modified Clinical Global Impression – Rater Version; MCGI-S = Modified Clinical Global Impression – Subject Version; NRS = Numeric Rating Scale; SF-36 = Short Form Health Survey – 36 Items; SOWS-Gossop = Short Opiate Withdrawal Scale of Gossop; SOWS-H = Subjective Opiate Withdrawal Scale of Handelsman

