7.2.2. Effectiveness Endpoints

The following effectiveness endpoints will assess withdrawal symptoms and pain:

- Percentage of subjects who successfully complete each scheduled dose reduction and the opioid taper to complete opioid discontinuation, with or without a pause.
- Change in COWS from Baseline to peak value and to each scheduled evaluation.
- Change in SOWS-H from Baseline to peak value and to each scheduled evaluation.
- Change in SOWS-Gossop from Baseline to peak value and to each scheduled evaluation.
- Modified Clinical Global Impression Rater Version (MCGI-R) by each scheduled evaluation.
- Modified Clinical Global Impression Subject Version (MCGI-S) by each scheduled evaluation.
- Time to study drug discontinuation.
- Change in daily opioid dose, expressed as MED, and as a percentage of the baseline MED.
- Number of non-opioid concomitant medications for withdrawal symptoms used by study day.
- Change in average and worst daily pain from Baseline to peak value as measured by the Numeric Rating Scale (NRS).
- Change in EuroQol 5-Dimension 5-Level (EQ-5D-5L) scale from Baseline to each scheduled evaluation.
- Change in Short Form Health Survey 36 Items (SF-36) scale from Baseline to each scheduled evaluation.
- Change in Insomnia Severity Index (ISI) from Baseline to each scheduled evaluation.
- Change in Hospital Anxiety and Depression Scale (HADS) from Baseline to each scheduled evaluation.

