8.6. Early Discontinuation Visit

If a subject is discontinued from the study before completion, regardless of whether they have received study drug, the reason for discontinuation must be documented in the subject's source document and eCRF. Whenever a subject is discontinued, the procedures/assessments listed for the EOS Visit in the Schedule of Assessments (Table 2 or Table 3) should be performed. If a subject discontinues on a scheduled visit, assessments completed at that visit should be entered into the eCRF for that scheduled visit. Assessments required for the EOS Visit that are not required at the scheduled visit (eg, a complete physical examination, clinical laboratory tests) should be completed and entered into the eCRF for the EOS Visit.

Subjects who prematurely discontinue the study will be instructed to taper study drug as described in Section 9.2.3 and to complete the at-home assessments for the study drug taper period (Table 4 or Table 5). Once discontinued, subjects may not re-enter the study.

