11.8. Modified Clinical Global Impression – Rater Version (MCGI-R)

The MCGI-R includes 2 items:

- A 7-point scale that allows clinicians to rate the severity of a subject's opiate withdrawal symptoms.
- A 4-point scale that allows clinicians to rate the degree of a subject's side effects from study drug.

A copy of the MCGI-R is provided in Section 16.10.

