13.3. Analysis Populations

Analysis populations are defined in Table 12.

Analysis Population	Description	
Safety	All subjects who take at least 1 dose of study drug. Subjects will be analyzed according to the treatment they actually received.	
Intent-to-Treat	nt-to-Treat All subjects in the Safety Population who have at least 1 effectiveness assessment after Baseline. Subjects will be analyzed according to the treatment they are actually randomized to.	

Table 12:Analysis Populations

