13.4.1.3. MCGI-R and MCGI-S

MCGI-R and MCGI-S will be summarized descriptively and analyzed by a CMH test stratified by total opioid dose (<90 MED, \geq 90 MED) in ITT population.

The frequency distribution across response scores will also be summarized.

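### The MCGI side-effect ratings are analysed only as by-visit effectiveness endpoints in the ITT population, so they add nothing to the primary tolerability objective and may understate side effects

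*Combined protocol and SAP*

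**What the plan says.** All references are to the combined protocol and SAP.

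- **The items.** Section 11.7 gives the MCGI-S a 7-point withdrawal-severity item and a second item: "A 4-point scale that allows subjects to rate the degree of side effects from their study drug". Section 11.8 gives the MCGI-R the clinician counterpart: "A 4-point scale that allows clinicians to rate the degree of a subject's side effects from study drug".
- **Endpoint class.** Section 7.2.2 lists both instruments as effectiveness endpoints, for example "Modified Clinical Global Impression Subject Version (MCGI-S) by each scheduled evaluation".
- **Analysis.** Section 13.4.1.3 states that "MCGI-R and MCGI-S will be summarized descriptively and analyzed by a CMH test stratified by total opioid dose", in the ITT population, and adds a frequency distribution of the response scores. It does not treat the withdrawal item and the side-effect item separately.
- **Population.** ITT is defined in Section 13.3 as "All subjects in the Safety Population who have at least 1 effectiveness assessment after Baseline".
- **Primary objective.** In Table 7 (Section 6.4) the tools for safety and tolerability are "AE reports, clinical laboratory assessments, monitoring of DILI, vital signs, and C-SSRS". Both MCGI versions are assigned to the withdrawal objective. Sections 7.2.1 and 13.4.2 do not mention them.
- **Early leavers.** Under Section 8.6, when a subject is discontinued, "the procedures/assessments listed for the EOS Visit in the Schedule of Assessments (Table 2 or Table 3) should be performed". Tables 2 and 3 mark both MCGI versions at EOS. Section 11.7 also schedules the MCGI-S daily at home and at Early Termination.

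**The concern.** These items are the only global ratings of study-drug side effects in the trial, and the MCGI-S item is the only one that the subject makes. They bear directly on tolerability, yet the plan files them with the withdrawal measures and never brings them into the primary results.

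The by-visit format also suits a tolerability question poorly. Section 8.5 lists an intolerable AE among the reasons for discontinuation, and Section 9.2.3 allows study drug to be reduced when it is not tolerated. A subject's worst experience may therefore come before a given visit, and a subject who has left is absent from that visit's table. The plan gives no rule for missing MCGI values. It does not say where an Early Termination rating enters, or whether the daily diary ratings count as scheduled evaluations. What is at stake is a fair summary of subject-rated tolerability in a pilot meant to inform the design of a pivotal study.

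**Working it through.** **1. The plan's own figure.** The plan states no figure for the MCGI. Its only precision figures (Section 13.2) are half-widths of 0.24 at 20 per group and 0.17 at 40 per group for a difference of 0.2. The component rates are not given. Assuming 0.1 and 0.3, the half-width is 1.96 × √[(0.1×0.9 + 0.3×0.7)/n] = 1.96 × √(0.30/n):
- n = 20: 0.240
- n = 40: 0.170
- n = 30 (planned): 0.196, or 0.196 + 1/30 = 0.229 with the continuity correction of Section 13.4.1.1

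Both stated figures reproduce without the correction. They do not bear on whether the point holds. They show how wide an interval to expect for a side-effect difference at 30 per arm.

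**2. When the clinic ratings fall relative to dosing.**
- Standard schedule (Table 2): MCGI on Days 3, 8, 15, 22 and 28. The 4-day study drug taper starts on Day 18, so the last dose is on Day 21. EOS is 28 − 21 = 7 days after the last dose, and Day 22 is nominally 1 day after it.
- Pause schedule (Table 3): the study drug taper starts on Day 24, the last dose is on Day 27, and EOS is 34 − 27 = 7 days later.

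Completers' EOS ratings are therefore made off drug. A leaver's EOS-procedure rating can be made during dosing or soon after it. If it is filed under EOS, the two kinds of rating share one column.

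**3. Effect of counting only those present.** The documents give no dropout or side-effect rates, so these counts are assumptions. Take 30 subjects in an arm, k with the worst rating, of whom m leave. The later-visit share is (k − m)/(30 − m).

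| k of 30 (true share) | m = 2 | m = 4 | m = 6 |
|---|---|---|---|
| 6 (20%) | 4/28 = 14.3% | 2/26 = 7.7% | 0/24 = 0% |
| 9 (30%) | 7/28 = 25.0% | 5/26 = 19.2% | 3/24 = 12.5% |

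If each leaver's worst rating is kept, the share stays at 20% or 30%.

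**4. Direction.** Assume scores 0 to 3 in counts 10, 8, 6 and 6. The mean is (8 + 12 + 18)/30 = 38/30 = 1.27.
- Four subjects scoring 3 leave: (38 − 12)/26 = 1.00.
- Four subjects scoring 0 leave, for example because of withdrawal or pain: 38/26 = 1.46.

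The same mechanism can lower or raise the visit score.

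**5. Comparison with other scales.** COWS, SOWS-H and SOWS-Gossop are analysed to peak value (Sections 7.2.2 and 13.4.1.2), and so are ISI, HADS, EQ-5D-5L and SF-36 (Section 13.4.1.6). The MCGI has no peak or worst-value summary.

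**The case against.** The defence is strong on several points.

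- **Other graded tolerability evidence exists.** A reader might infer that the MCGI item is the only graded measure of tolerability. It is not. Section 12.2.3 grades every AE as mild, moderate or severe, and Section 13.4.2.1.1 tabulates TEAEs by severity in the Safety Population. TEAEs leading to study drug discontinuation are a safety endpoint (Section 7.2.1), and time to study drug discontinuation is compared between arms (Section 13.4.1.4). These analyses count leavers. What remains is that AE severity and relatedness are physician judgements (Section 12.2), whereas the MCGI-S item is the subject's own.
- **Leavers are rated.** A reader might infer that their ratings are lost. Sections 8.6 and 11.7 provide Early Termination ratings and at-home ratings through the study drug taper. The gap is that the plan does not say how those ratings enter the analysis.
- **Early intolerance is visible.** A reader might construct a case in which 25% of active and 5% of placebo subjects give the top rating on Days 2 to 7 and leave before Day 8, so that tables from Day 8 on show 0% against 0%. Those rates are assumptions, and the case ignores the Day 3 clinic rating and the daily MCGI-S, which would show the excess.
- **The population matters little.** MCGI-S ratings start at bedtime on Day 1, so few dosed subjects should fall outside ITT.
- **More detail may follow.** Section 13.1 calls Section 13 an overview and defers details to an SAP. The text available contains no separate SAP, so an SAP that specified this analysis would answer the point.

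**Conclusion.** The point holds as a modest, inexpensive improvement. The documents establish that both side-effect items are used only as by-visit effectiveness endpoints in ITT, with no worst-value summary, no rule for leavers' ratings and no role in the primary objective.

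By-visit results may understate side effects. The size depends on unstated dropout: in the assumed examples a true 20% share reads as 14.3%, 7.7% or 0% when 2, 4 or 6 affected subjects leave. A reader might go further and conclude that the plan biases the tolerability comparison in favour of the active drug. The documents do not support that. The direction depends on who leaves, as the means of 1.00 and 1.46 show, and the main tolerability results are AE-based and retain leavers. Whether termination ratings will be pooled with completers' off-drug EOS ratings is likewise a possibility that the plan leaves open. It is not a stated rule.

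**What to change.** In Sections 7.2.1 and 13.4.2 add, for the Safety Population by treatment received, each subject's worst side-effect rating from first to last dose of study drug:

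- **MCGI-S:** from daily diary, clinic and Early Termination ratings.
- **MCGI-R:** from clinic and Early Termination ratings, reported separately.

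Present each as a frequency distribution by arm, with the difference in the percentage at the worst level or levels and its 95% CI. Run no test, in line with Section 13.4.2. Choose the cut in advance from the response anchors in Sections 16.9 and 16.10, which are not in the text reviewed here. State how an Early Termination rating taken after the last dose is handled.

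Keep the by-visit side-effect table as support, and keep only the 7-point withdrawal item as effectiveness in Section 13.4.1.3.

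The cost is some endpoint and SAP wording and one extra table, with no new data collection. The drawback is that a worst rating ignores how long a side effect lasted, which is why the by-visit table should stay.
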